8. EVALUATION DATA SOURCES AND PROCEDURES

a. Brief online questionnaire at registration

All participants will complete an online survey at registration. The survey will cover sociodemographics and injecting drug use history.

b. Follow up call at 7 days

SHIL will follow up with phase 1 people who receive an HIV or HCV detected test result one week after receiving their results via a telephone call, as part of the standard of care that would include provision of assistance, support and linkage to care services for newly diagnosed people. Sites managing their own results will be responsible for ensuring people are linked to follow up care and treatment as necessary. SHIL will follow up people with detected results in the case that sites have elected for SHIL to manage results."

c. Follow-up evaluation processes

Consent to participate in the follow-up evaluation processes will be requested at the time of registration as per procedures used in a range of other previous studies. Follow-up information will be collected via a variety of methods, for example a cross-sectional survey of participants or semistructured interviews and will include questions about acceptability of self-sampling, testing preferences and confidence regarding the performance of self-sampled DBS HIV or HIV/HCV test. Follow-up of both registrants who have sent a DBS kit for testing and those who do not complete DBS testing will occur to better understand the factors influencing completion of DBS testing by individuals who register for the service. A formal evaluation of the pilot is planned from December 2022. Further detail regarding the follow-up of participants will be provided to relevant Human Research Ethics Committees as an additional amendment as soon as possible. Follow-up of participants will not commence until formal ethics approval has been granted for this process.

d. Cost

The evaluation objective assessing cost (costs per test and costs per HIV or HCV infection diagnosed) relates to all costs relating to staffing, delivery DBS HIV testing kits, laboratory testing and result

communication and follow-up. The cost of staff wages will be estimated using data from the participating centres. Data on the cost of the DBS kit and laboratory testing will be sourced from the NSW State Reference Laboratory for HIV, St Vincent's Hospital, Sydney and includes the DBS collection kit, postage, labour, reagents, consumables and specimen storage. A cost pathway will be developed, outlining all steps involved and costs collated in an Excel spreadsheet.

9. SAMPLE SIZE

The sample size will focus on the primary objective of the program of reaching priority populations who are testing infrequently. Based on behavioural surveys, we assume that 19% of gay men had their last HIV test >2 years ago or never (34) and among CALD populations, 40% had never tested (16). Therefore to determine if the DBS pilot study is able to reach a 5% or greater proportion of infrequent testers than behavioural surveys, then at least 400 gay and bisexually active men and at least 460 heterosexuals from CALD populations is required.

An additional 1000 dual HIV/HCV tests will be available in Phase 2.

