3.2. NUMBER OF PARTICIPANTS

Phase 1: Based on sample size calculations (section 9), the minimum number of participants required to determine that the program is reaching 10% or more infrequent testers (tested >2 year ago or never) than behavioural surveys is 400 gay and bisexually active men and 460 heterosexual people from CALD populations (860 in total). These individuals may undergo repeat testing and thus the total number of DBS tests, particularly in gay and bisexually active men, may be greater.

Phase 2: To accommodate Phase 2, an additional 1000 testing kits will be included, for a total of 1,860 across all population groups.

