7. EVALUATION OUTCOMES AND DEFINITIONS

The key study outcomes and their definitions are listed below

- 1. **Return rate:** proportion of DBS samples which were returned for testing. This will also be disaggregated by target population.
- 2. **HIV test positivity rate:** The numerator for calculating HIV positivity is the number of laboratory confirmed HIV positive individuals with Western Blot testing. The denominator is the number of individual 4^{thd} generation EIA tests performed during the pilot period.
- 3. **HCV test positivity rate:** The numerator for calculating HCV positivity is the number of laboratory confirmed HCV positive individuals with RNA testing on the Hologic Panther analyser. The denominator is the number of individual HCV RNA tests performed during the pilot period.
- 4. **Proportion of participants who are infrequent testers:** The proportion of DBS participants who reported at the first registration they had never tested for HIV before or had tested over 2 years

ago. This outcome measure will also be disaggregated by target population and test combination (HIV only compared to HIV/HCV dual testing).

- 5. Linkage to care rate: proportion of DBS participants who return an HIV detected test result and are reviewed by a referral clinician within 2 weeks of diagnosis. Linkage to care will be verified by the registered nurse making the follow-up call to newly diagnosed participants one week after notification of results, and information will be self-reported by the participant. Linkage to care will be reported separately for participants who receive a reactive HIV result, and those who receive a reactive HCV RNA test result.
- 6. **Mean CD4 count at diagnosis:** calculated in laboratory confirmed HIV positive individuals using flow cytometry
- 7. Re-testing rate: Proportion of DBS participants who had two or more DBS tests in the study period
- 8. Acceptability of DBS test process: Proportion of DBS participants who reported they found the DBS testing processed acceptable or highly acceptable
- 9. Cost per DBS test conducted: the costs to the health system of each DBS test done
- 10. **Cost per HIV infection diagnosed** by DBS test: the costs to the health system of each positive DBS test
- 11. **Cost per HCV infection diagnosed** by DBS test: the costs to the health system of each positive DBS test

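### The 40% benchmark for CALD heterosexuals counts only people never tested for HIV, while the outcome compared with it also counts people last tested over 2 years ago, so the comparison can show a gain in reach where there is none.

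*Protocol*

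**What the plan says.** Section 9 of the protocol, repeated in the synopsis, sizes the HIV part of the pilot on a comparison with behavioural surveys. It gives the two benchmarks in one sentence: "19% of gay men had their last HIV test >2 years ago or never (34) and among CALD populations, 40% had never tested". The stated aim is to find out whether the programme can "reach a 5% or greater proportion of infrequent testers than behavioural surveys", with at least 400 gay and bisexually active men and at least 460 CALD heterosexuals.

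Section 3.2 describes the same 400 and 460 as enough to show that the programme is "reaching 10% or more infrequent testers (tested >2 year ago or never) than behavioural surveys". The definition in its bracket applies to both groups.

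Outcome 4 in section 7 is the quantity to be measured: "The proportion of DBS participants who reported at the first registration they had never tested for HIV before or had tested over 2 years" ago. The section adds: "This outcome measure will also be disaggregated by target population and test combination". The CALD result is therefore the composite too. The protocol gives no composite survey figure for CALD populations, and it lists no outcome restricted to people who never tested.

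**The concern.** A programme proportion can be set against a survey proportion only if both count the same people. For gay men they do. For CALD heterosexuals the programme figure includes everyone whose last test was more than 2 years ago, and the benchmark leaves them out.

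The error has one direction. Never tested is a subset of the composite, so the mismatch can only favour the programme. A pilot that recruited exactly the population described by the survey would exceed 40% in expectation whenever some ever-tested CALD people had gone more than 2 years without a test.

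Reaching people who test infrequently is the programme's stated primary objective and the stated basis of the sample size. A spurious excess would credit the pilot with reach into a group that section 1.1 describes as more likely to be diagnosed late.

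**Working it through.** **Inputs from the protocol.** CALD benchmark 40%, never tested (section 9). CALD sample size 460 (sections 3.2 and 9). Margin 5 points in section 9 and 10 points in section 3.2; both are carried below. Outcome: never tested or last tested over 2 years ago (section 7, outcome 4).

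**Input not in the protocol.** f, the share of ever-tested CALD people whose last test was over 2 years ago. It is an assumption, shown as a range.

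**The plan's own sample sizes.** Significance level, sidedness and power are not stated. A one-sample test for +5 points, one-sided 5%, 80% power, gives 404 from 19% but 600 from 40%. None of the settings tried gave both 400 and 460. Nothing below depends on how 460 was derived.

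**Like-for-like benchmark.** Composite = 0.40 + 0.60 × f.

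- f = 5%: 0.40 + 0.030 = 43%
- f = 10%: 0.40 + 0.060 = 46%
- f = 20%: 0.40 + 0.120 = 52%

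The mismatch alone produces the 5-point margin when 0.60 × f = 0.05, so f = 8.3%. It produces the 10-point margin when f = 0.10/0.60 = 16.7%.

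**What a programme with no gain would show.** Take X ~ Binomial(460, composite). A result of 45% or more means X ≥ 207, and 50% or more means X ≥ 230. These two columns need no significance test. The last column assumes a one-sample, two-sided 5% test against 40%. Its critical value is 0.40 + 1.96 × √(0.40 × 0.60/460) = 0.4448 by normal approximation, or X ≥ 206 by the exact binomial.

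| f | Composite | P(45% or more) | P(50% or more) | P(significant excess): exact / normal |
|---|---|---|---|---|
| 0 | 40% | 1.7% | under 0.1% | 2.1% / 2.5% |
| 5% | 43% | 21% | 0.2% | 23% / 26% |
| 10% | 46% | 68% | 5% | 72% / 74% |
| 20% | 52% | 99.9% | 82% | 99.9% / 99.9% |

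**Where f might lie.** The only related figures in the protocol are for gay men: about 10% never tested (section 1.1) and 19% on the composite (section 9). They give f = (19 − 10)/(100 − 10) = 10%. The two figures cite different survey years and a different population, so this is only an illustration.

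**Effect on sample size.** With a two-sided 5% level and 80% power (both assumed), a one-sample test for +5 points needs 761 from 40%, and 774, 782 and 780 from 43%, 46% and 52%. Correcting the definition moves the benchmark and hardly changes the number needed.

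**The case against.** The strongest reply is that the protocol contains no decision rule to be misled. Section 10 plans descriptive proportions and chi-squared tests between strata, and names no test against 40%. Reach is a secondary evaluation objective, and the benchmark appears only in the sample-size rationale. This stands in part: the significance probabilities describe a test that is assumed. It does not remove the defect. Section 9 says the sample is meant to determine whether the programme exceeds the surveys, and a purely descriptive comparison with 40% carries the same bias.

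The second reply is that the size is unknown, and this stands. A reader might infer that the pilot would probably report a gain in the CALD group with none present. The documents do not support that. Against 45%, the chance passes one half only once f reaches about 8%; at f = 5% it is 21%. Against the 10-point margin of section 3.2, it is 5% even at f = 10%. The comparison can mislead; how likely that is depends on a figure that the protocol does not give.

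A reader might also infer that outcome 4 overstates reach because it is asked at registration and so includes people who never return a kit. That would need infrequent testers to return fewer kits than others, and no section says so; the difference could run the other way. Registrants and people tested are both legitimate denominators. Return rate is already outcome 1, reported by target population, and section 8 plans follow-up of registrants who do not complete testing. No change of denominator is called for.

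**Conclusion.** The mismatch is in the text and its direction is certain: as written, the CALD comparison can only flatter the programme. Its size is 60% × f. That is 3, 6 and 12 percentage points for f of 5%, 10% and 20%, and an f of 8.3% alone supplies the whole 5-point margin of section 9. These sizes assume that the programme draws exactly the surveyed population and that f lies in the range shown. The comparison for gay men is not affected, since benchmark and outcome share one definition. The point should be corrected before any CALD reach result is reported against 40%.

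**What to change.** In sections 7 and 9, and in the synopsis:

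- Report never tested and last tested more than 2 years ago as separate categories of outcome 4.
- For CALD heterosexuals, compare only the never-tested proportion with 40%.
- Report the CALD composite without a benchmark, unless a composite figure is obtained from the source survey; in that case use that figure.

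The sample-size statement has to be reworded so that the CALD quantity is the never-tested proportion, with one margin stated in both section 3.2 and section 9.

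Cost: a few sentences, and no more participants on this account. The CALD figure set against the benchmark will be less favourable. The change also requires that the registration data hold the two categories separately. The registration form is not shown and the website launched in November 2016, so this should be checked first. If the categories were pooled, the never-tested proportion cannot be recovered for past registrants by rewording, and a composite figure from the source survey would be needed.

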	For settings-based DBS testing (phase 2), settings will be able to provide DBS testing kits to participants who meet the eligibility criteria where they also access a service for which any of the following situations may apply:
	 Service is unable to collect conventional venepuncture specimens. For example, a remote outreach service, community health setting or opling cotting
	 The storage and transport of conventional specimens is problematic The potential risk of blood contamination prohibits sampling of conventional venepuncture specimens, for example, in outreach settings such as sex on premises venues (SOPV)
Study procedures	Information relating to the pilot and the online registration form will be made available on a dedicated website managed by the DBS Project Coordinator. Self-sampling dried blood spot (DBS) kits will be distributed via two pathways:
	1. A 'postal pathway' (phase 1), and;
	2. A 'settings pathway' (phase 2).
	Phase 1 of the pilot will involve individuals self-registering online to receive a DBS kit to a nominated address via post. Registration and kit return, will be the same for both distribution pathways. The NSW State Reference

	Laboratory for HIV, St Vincent's Hospital, Sydney will be the organisation responsible for receiving and testing all DBS samples, and clinical governance, result provision and follow-up will be provided by NSW Sexual Health Infolink (SHIL). Some settings (phase 2 sites) may elect to provide results directly to participants; however SHIL will maintain overarching clinical governance and will monitor follow up. Monitoring and evaluation will be overseen by the NSW Ministry of Health with input from the investigator group.
Statistical considerations	The sample size will focus on the primary objective of the program of reaching high-risk populations who are testing infrequently. Based on behavioural surveys, we assume that 19% of gay men had their last HIV test more than 2 years ago or never, and among CALD populations 40% had never tested. Therefore, to determine if the DBS program is able to reach a 5% or greater proportion of infrequent testers than behavioural surveys, then at least 400 gay and bisexually active men and at least 460 heterosexuals from CALD populations is required for HIV testing. An additional 1000 dual HIV/HCV tests will be performed.

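### The same 400 and 460 participants are tied to a 5% excess of infrequent testers in two places and to 10% in a third, and 460 is too few for 5 points

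*Protocol*

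**What the plan says.** Protocol section 9 takes two benchmarks from behavioural surveys: 19% of gay men last tested for HIV more than 2 years ago or never, and 40% of CALD populations never tested. It then gives the aim, "Therefore to determine if the DBS pilot study is able to reach a 5% or greater proportion of infrequent testers than behavioural surveys", and the numbers, "at least 400 gay and bisexually active men and at least 460 heterosexuals from CALD populations is required".

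The synopsis (Statistical considerations) repeats the same target, "to determine if the DBS program is able to reach a 5% or greater proportion of infrequent testers than behavioural surveys", with the same 400 and 460.

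Section 3.2 presents its minimum as coming from the section 9 calculation. It gives the same 400 and 460 (860 in total) as the number "required to determine that the program is reaching 10% or more infrequent testers (tested >2 year ago or never) than behavioural surveys".

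None of the three places states a significance level, one- or two-sided testing, a power, or whether the survey figure is a fixed value or a second sample with its own error.

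**The concern.** One pair of sample sizes cannot be the stated minimum for both a 5% and a 10% excess under the same assumptions. Section 3.2 cites section 9 for a figure that section 9 does not contain, so at least one place is wrong.

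This is the only sizing rationale for the main study; the venepuncture sub-study has its own. The two targets lead to different claims. Under 10 points the numbers are ample or adequate. Under 5 points the CALD group in particular is short. Someone who reads only the synopsis would take a 5-point gain in reach to be reliably detectable, and could then give too much weight to a non-significant result in that group.

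**Working it through.** **Inputs from the protocol.** Benchmarks p0 = 0.19 and 0.40; n = 400 and 460 (section 9); excess d = 0.05 (section 9, synopsis) or 0.10 (section 3.2).

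**Assumptions, because the protocol is silent.** Alpha 0.05, one- or two-sided; percentages read as percentage points, so p1 = p0 + d.

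**Formulas** (q = 1 − p, p̄ = (p0 + p1)/2):

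- One-sample, survey figure fixed: n = [z_a√(p0q0) + z_b√(p1q1)]² / d²; power = Φ{[d√n − z_a√(p0q0)] / √(p1q1)}.
- Two-sample, equal groups, n per group: n = [z_a√(2p̄q̄) + z_b√(p0q0 + p1q1)]² / d²; power = Φ{[d√n − z_a√(2p̄q̄)] / √(p0q0 + p1q1)}.
- Continuity correction: n' = (n/4)[1 + √(1 + 4/(nd))]².

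**Step 1. Try to reproduce 400 and 460.**

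| Rule | Gay and bisexually active men (stated 400) | CALD (stated 460) |
|---|---|---|
| +5, one-sample, one-sided, 80% | 404 | 600 |
| +5, one-sample, two-sided, 80% | 510 | 761 |
| +5, two-sample, two-sided, 80% | 1,059 | 1,534 |
| +10, one-sample, two-sided, 80% | 133 | 191 |
| +10, two-sample, two-sided, corrected, 80% | 305 | 408 |
| +10, same, 85% | 346 | 463 |
| +10, same, 90% | 401 | 538 |

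No row gives both. The 400 is close to a 5-point rule (404) and to a 10-point rule (401). The 460 is close only to a 10-point rule at a different power (463). Powers of 80% to 95%, survey samples 2 to 10 times larger, relative differences and interval precision were also tried. None gave both numbers.

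**Step 2. Power at +5 points with the stated n.**

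CALD, 40% to 45%, n = 460 (√n = 21.448, d√n = 1.0724, √(p0q0) = 0.4899, √(p1q1) = 0.4975):

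- One-sample, two-sided: (1.0724 − 1.960 × 0.4899)/0.4975 = 0.226, power 58.9% (exact binomial 56%).
- One-sample, one-sided: (1.0724 − 1.645 × 0.4899)/0.4975 = 0.536, power 70.4% (exact 70%).
- Two-sample, two-sided, equal-sized survey: (1.0724 − 1.960 × 0.6991)/0.6982 = −0.427, power 33.5%.

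Gay and bisexually active men, 19% to 24%, n = 400 (d√n = 1.000, √(p0q0) = 0.3923, √(p1q1) = 0.4271):

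- One-sample, two-sided: (1.000 − 1.960 × 0.3923)/0.4271 = 0.541, power 70.6% (exact 66%).
- One-sample, one-sided: (1.000 − 1.645 × 0.3923)/0.4271 = 0.831, power 79.7% (exact 78%).
- Two-sample, two-sided, equal-sized survey: (1.000 − 1.960 × 0.5810)/0.5799 = −0.239, power 40.5%.

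**Step 3. Power at +10 points, two-sided, normal approximation.** One-sample: 99.7% (400) and 99.1% (460). Two-sample: 91% and 86%.

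**Step 4. Smallest excess detectable with 80% power, two-sided.** One-sample: 5.7 points (400) and 6.5 points (460). Two-sample: 8.4 and 9.2 points.

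**The case against.** The strongest reply concerns the 400. The question in section 9 is directional and the benchmark is an assumed value, so a one-sample, one-sided 5% test is a natural reading. That test needs 404 for 80% power at +5 points, so the 400 is consistent with 5 points. This stands: the shortfall cannot be asserted for both groups under every reading. It does not rescue the 460. The same rule needs 600 there, and a fixed benchmark is the most favourable comparator, because sampling error in the survey only lowers power.

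A reader might infer the reverse, that the numbers show 10 points was intended. The document does not support that. The 10-point match needs 90% power for one group (401) and 85% for the other (463), and the protocol gives no power at all. Two of the three places, including the sample-size section itself, say 5%.

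It can also be said that this is a pilot, that its primary evaluation objective is feasibility (section 2), that its analyses are largely descriptive, and that the numbers are minima. That limits the consequences. Even so, section 9 sizes the study on reaching infrequent testers, and the contradiction remains.

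Two further inferences should not be added. First, section 10 names chi-squared tests only between strata. The test against the survey figure may be in a statistical analysis plan that was not available, so its absence is not counted here. Second, section 3.2 says openly that "an additional 1000 testing kits will be included, for a total of 1,860 across all population groups". Adding kits to participants is loose labelling, but no power claim rests on the total. Nor can the 59% return in the UK postal pilot (section 1.1) be carried over to kits meant for settings, where testing may be assisted on site.

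**Conclusion.** The contradiction is established from the text alone: the same 400 and 460 serve a 5% excess in the synopsis and section 9 and a 10% excess in section 3.2. The error parameters and the comparator are unstated, and which difference was intended cannot be settled from the protocol.

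The numerical conclusion is firm only for the CALD group. At alpha 0.05, 460 reaches no more than about 70% power for +5 points under any variant tried. For 400, adequacy at +5 points depends on the unstated choices. At +10 points both groups are adequately powered.

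These figures rest on alpha 0.05 and on reading the percentages as points. If 5% were relative, two-sided one-sample power would be only about 7% and 14%. They also take 40% as the CALD benchmark, as section 9 does, although that is the share never tested and the section 7 outcome also counts people tested over 2 years ago.

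**What to change.** Retrieve the original calculation and confirm the intended difference. Then make the synopsis, section 3.2 and section 9 agree, say that the difference is in percentage points, and state alpha, sidedness, whether the survey figure is fixed or a sample, and the power achieved with 400 and 460.

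- If 10 points was intended, correct the synopsis and section 9.
- If 5 points is kept, correct section 3.2 and state the lower power plainly, above all for the CALD group (about 59% two-sided or 70% one-sided against a fixed benchmark).

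The cost is wording in up to three places and, on either branch, a less favourable claim about what the pilot can detect. No participants need to be added.
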